Study Protocol

Can a dedicated chronic limb-threatening ischaemia (CLTI) clinic improve patient self-reported quality of life?

Protocol v 1.6

Date: 14/11/2022

This protocol has regard for the HRA guidance.

1. Background

Chronic limb-threatening ischaemia (CLTI) is the most severe form of peripheral arterial disease (PAD). It affects 1% of the population and its incidence is expected to rise. It is a condition where the circulation to one, or both limbs is inadequate. It requires investigation and may require surgery in order to improve the blood flow to the affected limb(s). Without improvement in circulation, ulcers and gangrene set in, and the only cure is a major limb amputation.

Vascular surgery units in the United Kingdom have undergone centralisation into regional networks over the last decade in order to consolidate vascular surgery into 'high volume centres' to provide high quality care and better outcomes for patients.

However, national analysis of the performance of units has demonstrated that only 50% of CLTI patients are revascularised within the 'deliberately-challenging timeline' issued by the Vascular Society of Great Britain and Ireland (Birmpili et al., 2021; Vascular Society of Great Britain and Ireland, 2019).

CLTI already comprises more than 50% of vascular unit workload and the prevalence of CLTI is expected to rise, further increasing the burden on vascular services (Fowkes et al., 2016; Vascular Society of Great Britain and Ireland, 2018, 2021).

There is ample evidence demonstrating a strong inverse correlation between the provision of specialist outpatient clinics in the assessment and management of diabetic foot ulcers and major lower limb amputation (Joret et al., 2019; M Kerr, Rayman, & Jeffcoate, 2014; Marion Kerr, 2017; Monteiro-soares, Vale-lima, Martiniano, Dias, & Boyko, 2021; Paisey et al., 2017). Diabetic foot ulceration is a condition which has significant overlap with CLTI. It could therefore be inferred that a similar service for CLTI patients would also confer the same benefits.

As many as 50% of CLTI patients also suffer from a significant degree of frailty, which makes treating patients with the condition more perilous (Houghton et al., 2021). The current guidance from the Vascular Society of Great Britain and Ireland recommends that patients who suffer with frailty should have access to elderly medicine specialists who can help with optimisation, complex decision making or advanced care planning. There is growing evidence that these services have

tangible benefits for vascular patients (Gordon, Evans, & Dhesi, 2017; J. Partridge, Sbai, & Dhesi, 2018; J S L Partridge et al., 2017; Judith S L Partridge et al., 2015)

At the Leeds Vascular Institute, we have implemented a dedicated CLTI clinic to assess and manage patients with the condition. Whilst there is limited evidence that these rapid access clinics can facilitate review and management of the condition, thereby successfully preventing major amputation in CLTI patients, the results are typically from single centre data series (Khan et al., 2020; Nickinson et al., 2021). There is a paucity of evidence evaluating patient opinions of this type of service and none that demonstrate any impact on their quality of life.

Furthermore, we have integrated an elderly medicine service [Perioperative Medicine for the Older Person undergoing Surgery (POPS)] to facilitate clinic reviews, decision making, advanced care planning for elderly (aged > 65 years old), medically complex (1 or more seriously debilitating medical conditions) and/or frail (Rockwood Clinical Frailty Score > 5) vascular patients. The elderly medicine service exists as a separate entity from the CLTI clinic and sees vascular patients with any vascular pathology, including aneurysmal or carotid disease in addition to CLTI. However, a significant proportion of patients seen in the POPS clinic originate from the CLTI clinic. Our area of interest with this is specifically CLTI as evidence suggests that frailty is more prevalent amongst this cohort than aneurysmal patients.

2. Rationale.

As previously mentioned, there is good evidence to suggest that specialist outpatient clinics are associated with good limb salvage outcomes, both for diabetic and CLTI patients.

All of the evidence that supports the use of CLTI clinics has been focused on clinical outcomes, but to our knowledge, there is no study that exists which has evaluated the benefit of the service on patient self-reported quality of life.

Additionally, elderly and/or frail CLTI patients are referred into the POPS clinic to help with complex decision making and advanced care planning.

These services have been designed and implemented with patients in mind but there is no evidence which actually determines the impact of these services from the patient's perspective.

Patient reported outcomes are an important measurement of a quality service and it is seldom reported in surgery. There is some limited evidence to suggest that CLTI clinics will be favourably reviewed by patients (Khan et al., 2020), but no evidence at all to determine if they can improve quality of life.

3. Theoretical Framework

The aim with CLTI treatment is to achieve limb salvage, that is to prevent the leg from deteriorating to the point of necessitating amputation. Limb salvage is seen as the ultimate goal following CLTI intervention.

The assumption is that patients who have their leg successfully saved, and avoid amputation will have a better quality of life because of it. However this has not been formally identified.

The POPS service exists to improve care provided to the most complex and frail CLTI patients. An evaluation of the service in terms of its clinical impact is already underway, but again we lack any patient feedback on the service.

4. Research Question / Aim

4.1 Objectives

To evaluate the difference that CLTI clinic attendance and management has on patient-reported quality of life.

Additionally, we want to explore what CLTI patients referred into the POPS service feel about the service they have received, if it has been beneficial, helped them make complex decisions or provided more information on their condition.

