4.2 Outcome

We hypothesise that patients will have a statistically significant improvement in self-reported quality life after CLTI clinic assessment management in comparison to before CLTI clinic assessment and management.

We propose that the POPS service will be favourably reviewed by patients when provided with a structured questionnaire.

5. Study Design and Methods of Data Collection and Data Analysis

This will be a prospective observational repeated measures study.

Patients who are referred into the CLTI clinic will be identified from the clinic register, which also distinguishes between new patients and patients who are being followed-up.

New patients who are attending the CLTI clinic will be approached to enrol into the study. Patients who consent to enrolment in the study will have their details recorded on a register which will enable the researchers to identify when the next appointments are due and can therefore determine when the next questionnaire can be delivered.

If patients consent to participate, they will be asked to complete:

- Their first EuroQol-5D questionnaire immediately prior to their first CLTI clinic appointment
- 1 feedback survey about their CLTI clinic experience after their first appointment
- A second EuroQol-5D questionnaire 6-12 weeks after their treatment is complete
- A third EuroQol-5D questionnaire at 12 months after the initial appointment

Separately, patients who are then referred from CLTI clinics to the POPS service at (based on the POPS referral criteria) will be asked if they wish to answer a structured questionnaire about the POPS service. If they agree, they will be asked to complete:

- 1 additional feedback survey about their POPS clinic experience immediately after their appointment

This is in addition to the 4 questionnaires and surveys they have completed / will be asked to complete as part of the CLTI clinic evaluation.

The anticipated study start date is 1st December 2022, with primary completion expected around 1st July 2023. The expected study completion date is 1st July 2024.

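### The title and Section 4.1 ask what the CLTI clinic does to quality of life, but every participant attends it and the only contrast is before versus after, so the change cannot be attributed to the clinic

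*Protocol*

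**What the plan says.** - **Title:** "Can a dedicated chronic limb-threatening ischaemia (CLTI) clinic improve patient self-reported quality of life".
- **Section 4.1:** "To evaluate the difference that CLTI clinic attendance and management has on patient-reported quality of life".
- **Section 2:** the evidence gap is put in the same terms: "there is no study that exists which has evaluated the benefit of the service on patient self-reported quality of life".
- **Section 4.2:** the hypothesis is that "patients will have a statistically significant improvement in self-reported quality life after CLTI clinic assessment management", compared with before.
- **Section 5:** the study is observational with repeated measures. The EQ-5D is taken three times: "Their first EuroQol-5D questionnaire immediately prior to their first CLTI clinic appointment", then "A second EuroQol-5D questionnaire 6-12 weeks after their treatment is complete", then 12 months after the initial appointment.
- **Sections 6 and 7.1.1:** one centre, and eligibility rests on being a CLTI patient seen and enrolled in the clinic.
- **Sections 1 and 3, on the course of the disease:** "Without improvement in circulation, ulcers and gangrene set in, and the only cure is a major limb amputation". Treatment aims to "prevent the leg from deteriorating to the point of necessitating amputation".

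**The concern.** The title and Section 4.1 ask for an effect: quality of life with the clinic against quality of life without it. The protocol collects data only with the clinic. It describes no concurrent, historical or external comparator and no repeated pre-clinic baseline. The CLTI and POPS feedback surveys give no quality-of-life contrast.

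The within-patient change therefore combines any clinic effect with:

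1. the natural course of the disease, which Section 1 describes as deterioration unless circulation improves;
2. possible regression to the mean, because patients enter when newly referred;
3. for the title's question about a *dedicated* clinic only, treatment that patients might have received anyway.

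The direction of the bias is not known. An improvement could be reported as the answer to the title when the clinic contributed nothing. A real benefit that consists of deterioration avoided, which is how Section 3 frames the aim, could appear as no change and be read as failure.

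**Working it through.** **The plan's own figures.** Section 7.2 gives 50–100 patients on recruitment grounds. Three clinics a week with 3–4 new patients each give 9–12 a week, so 100 patients take 100/12 = 8.3 to 100/9 = 11.1 weeks, in line with the stated 10 or so. No EQ-5D mean, SD, correlation or effect size is given, so the size of the bias cannot be derived from the protocol.

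**What the design can identify.** Let *e* be the clinic effect and *b* the change that would have occurred without the clinic, both in SDs of the EQ-5D. The expected before-after change is *b* + *e*. Estimating *e* alone needs information on *b*, and none is collected.

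**Illustration; all inputs assumed.** Equal SDs before and after, approximately normal changes, before-after correlation ρ of 0.5 to 0.7, full follow-up, and a two-sided 5% paired t-test.

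- SD of the change = √(2(1 − ρ)): 1.000 at ρ = 0.5 and 0.775 at ρ = 0.7.
- Noncentrality = (*b* + *e*)√n / √(2(1 − ρ)). Example: *b* = 0.2, *e* = 0, n = 50, ρ = 0.5 gives 0.2 × 7.071 / 1.000 = 1.414. From the noncentral t, the chance of a significant improvement is 0.283.

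Chance of a significant improvement (ρ = 0.5 to ρ = 0.7):

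| Background *b* | Clinic effect *e* | n = 50 | n = 100 |
|---|---|---|---|
| +0.2 | 0 | 28.3–43.2% | 50.8–72.5% |
| +0.2 | 0.3 | 93–99% | >99% |
| 0 | 0 | 2.5% | 2.5% |
| 0 | 0.3 | 55–77% | 84–97% |
| −0.2 | 0 | <0.1% | <0.1% |
| −0.2 | 0.3 | 10–14% | 17–25% |
| −0.3 | 0 | <0.1% | <0.1% |
| −0.3 | 0.3 | 2.5% | 2.5% |

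Compare *e* = 0 with *e* = 0.3 only within one value of *b*. The study cannot tell which *b* applies.

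**Regression to the mean and decline together.** Suppose patients enter 0.3–0.5 SD below their usual level, so that they regain that amount times (1 − ρ), or 0.09–0.25 SD, against a 0.2 SD decline. With *e* = 0 the chance of a significant improvement is 0.2–5.3% at n = 50 and 0.0–7.1% at n = 100. With *e* = 0.3 it is 40–68% and 68–93%.

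**Sample size does not help.** The 95% half-width of the mean change is t(0.975, n − 1) × √(2(1 − ρ)/n): 0.22–0.28 SD at n = 50 and 0.15–0.20 SD at n = 100. If *b* may lie anywhere from −0.3 to +0.2, an observed change of 0.2 SD fits a clinic effect from 0.2 − 0.2 = 0 to 0.2 + 0.3 = 0.5 SD. The half-width shrinks with n; that 0.5 SD range does not.

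**The case against.** The strongest reply is that the operative text is already honest. Section 5 calls the study observational with repeated measures, and Section 4.2 words the hypothesis as after versus before. A single-group evaluation of a new service is legitimate, and nothing in the dissemination section promises a causal claim. On this view only loose wording in a title and one objective remains. That stands to this extent: Section 4.2 needs no change of hypothesis, and the remedy is to the wording, not the data collection. It does not remove the mismatch, because the title and Section 4.1 define the question the study says it will answer. An analysis plan cannot repair this either, since no data without the clinic are collected.

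Section 4.1 also says attendance *and management*, so treatment belongs to the effect it asks about. That is accepted: treatment received anyway counts as background for the title's question only, so *b* means something different for the two questions. Even the whole bundle cannot be separated from natural course and regression to the mean.

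The illustration is open to fair criticism. The only background direction the protocol itself supports is decline, and a gain of 0.2 SD is purely assumed. Entry is by diagnosis and attendance, not by a low EQ-5D score, so regression to the mean is only possible. When it is combined with a decline, the false-positive chance is mostly near or below nominal. The 0.5 SD range is simply the assumed width of *b*. These points limit what the numbers show about size. They leave the identification problem untouched, and under a decline the risk becomes a missed benefit.

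**Conclusion.** The concern holds and should be fixed. The design can estimate how EQ-5D changes in patients who attend the clinic; it cannot say how much of that change the clinic caused. This follows from the protocol's own eligibility rule and measurement schedule and needs no assumed figure. The size and sign of the bias in this study are unknown. The probabilities above rest on assumed background changes, effects and correlations, and show only that the error could go either way and that enlarging the sample does not cure it. The data remain useful as description.

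**What to change.** - **Title:** reword the question to: *How does self-reported quality of life change in patients managed through a dedicated CLTI clinic?*
- **Section 4.1, first sentence:** reword to: *To describe the change in self-reported EQ-5D, among patients managed through the CLTI clinic, from the pre-clinic questionnaire to the post-treatment and 12-month questionnaires.* The time points stay as set in Section 5.
- **Section 4.2:** keep the before-after hypothesis and add: *Because there is no comparator, this change will not be attributed to the clinic.*

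The cost is a less ambitious headline claim and, if approval has already been given, a notice of amendment to the REC under Section 8.1. No extra patients, visits or staff are needed. Keeping the causal question instead would require a comparator group, at much greater cost.

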4.2 Outcome

We hypothesise that patients will have a statistically significant improvement in self-reported quality life after CLTI clinic assessment management in comparison to before CLTI clinic assessment and management.

We propose that the POPS service will be favourably reviewed by patients when provided with a structured questionnaire.

5. Study Design and Methods of Data Collection and Data Analysis

This will be a prospective observational repeated measures study.

Patients who are referred into the CLTI clinic will be identified from the clinic register, which also distinguishes between new patients and patients who are being followed-up.

New patients who are attending the CLTI clinic will be approached to enrol into the study. Patients who consent to enrolment in the study will have their details recorded on a register which will enable the researchers to identify when the next appointments are due and can therefore determine when the next questionnaire can be delivered.

If patients consent to participate, they will be asked to complete:

- Their first EuroQol-5D questionnaire immediately prior to their first CLTI clinic appointment
- 1 feedback survey about their CLTI clinic experience after their first appointment
- A second EuroQol-5D questionnaire 6-12 weeks after their treatment is complete
- A third EuroQol-5D questionnaire at 12 months after the initial appointment

Separately, patients who are then referred from CLTI clinics to the POPS service at (based on the POPS referral criteria) will be asked if they wish to answer a structured questionnaire about the POPS service. If they agree, they will be asked to complete:

- 1 additional feedback survey about their POPS clinic experience immediately after their appointment

This is in addition to the 4 questionnaires and surveys they have completed / will be asked to complete as part of the CLTI clinic evaluation.

The anticipated study start date is 1st December 2022, with primary completion expected around 1st July 2023. The expected study completion date is 1st July 2024.

5.1 Data collection

Data will be collected using the standardised EuroQol-5D questionnaire. This is a validated patient reported outcome measure which has been widely used in studies evaluating self-reported quality of life.

A license to use the questionnaire has been authorised and granted. The EuroQol survey will be delivered electronically using LimeSurvey software. It can be completed by study participants, with or without prompting from their carers or relatives, or researchers on behalf of study participants.

Additionally a structured questionnaire evaluating the CLTI clinic and/or POPS service using a Likert scale and free text comments will be administered to participants. We plan to use an iPad or tablet to administer the surveys to patients.

Survey responses that are entered are stored electronically within LimeSurvey, both on an app and also on a website cache. The survey itself contains no identifiable information at all.

Identifiable data will only be kept on a study registry within a password protected cloud drive attached to an NHS.net account. NHS.net is Caldicott compliant and therefore adequate for handling patient identifiable data. The purpose of this registry is to ensure that subsequent survey responses from the same patients are linked together (as it is a repeated measures design) and also to highlight when new appointments are due. This information is not contained within the EuroQol survey.

6. Study Setting

The study will take place in the outpatient suite waiting room. Patients who are attending their first CLTI appointment and have consented to participate will be given the questionnaires on a tablet computer to complete. Identifying patients from the clinic register targets the exact demographic cohort. It is a single centre study. The POPS service is also in an outpatient suite.

7. Sample and Recruitment

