7.2 Sampling

We will adopt a convenience sampling strategy. The rationale for this strategy is the available pool of respondents who attend the CLTI clinic. We have chosen a sample size of between 50 – 100 patients. The CLTI clinic runs 3 times weekly and attempts to see 3-4 new patients per clinic, which means on average 9 – 12 patients per week. This would mean we should achieve our sample in around 10 weeks. However, pragmatically speaking, not every clinic will have the same number of new patients, not every patient will be suitable and some patients will be lost to follow-up. Hence we have a range of between 50 – 100 responses would be sufficient.

There is no set amount of structured feedback questionnaire responses required, either of the CLTI or POPS clinic.

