8.4 Data Protection and Patient Confidentiality

Personal information which could identify patients will be kept secure on a password secured registry contained on an NHS.net secure cloud drive. NHS.net is Caldicott compliant and is appropriate for handling sensitive data. The purpose of this is solely to identify patient appointments which allow for linking study responses as per the repeated measures study design.

The EuroQol-5D survey has no patient identifiable data at all, and the responses are stored on the LimeSurvey application.

The principal investigator will have access to the registry of patients with identifiable data. This will only be available to the Principal Investigator and Chief Investigator. Analysis can be performed by other members of the research team as it doesn't require any handling of sensitive data. Data will be stored for 5 years

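### Apart from baseline EQ-5D, no entry characteristics are listed for collection, so differences in age, frailty, diabetes or limb severity between patients lost and kept cannot be described or adjusted for

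*Protocol*

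**What the plan says.** Section 5.1 of the protocol gives the data items. The outcome is the EQ-5D: "Data will be collected using the standardised EuroQol-5D questionnaire". The other instrument is the service survey: "Additionally a structured questionnaire evaluating the CLTI clinic and/or POPS service using a Likert scale and free text comments will be administered to participants". Section 5 sets three EQ-5D time points, the first being "Their first EuroQol-5D questionnaire immediately prior to their first CLTI clinic appointment", so a baseline value is sought from everyone who consents.

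The identifiable registry is described twice. Section 5.1: "The purpose of this registry is to ensure that subsequent survey responses from the same patients are linked together", and to flag when appointments fall due. Section 8.4: "The purpose of this is solely to identify patient appointments which allow for linking study responses as per the repeated measures study design". Section 8.4 adds that analysts need no sensitive data.

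On loss, section 7.2 says that "not every patient will be suitable and some patients will be lost to follow-up", without a rate. On case mix, the Background says "As many as 50% of CLTI patients also suffer from a significant degree of frailty" and that this makes treatment riskier. Age and the Rockwood score appear only as features of the patients for whom the elderly medicine (POPS) service is intended.

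**The concern.** The hypothesis in section 4.2 is an improvement from before to after clinic management, with no control group. The change can be observed only in patients who return a later questionnaire. If frailer or more severely affected living patients respond less often and also improve less, the observed mean change is too large. Seeing and correcting this needs characteristics measured at entry in everyone, including those later lost. The planned data hold one such variable, the baseline EQ-5D.

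This cannot be left to a statistical analysis plan. Such a plan decides how data are analysed; it cannot supply fields that were not collected or widen a purpose that the protocol restricts.

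A second consequence does not depend on dropout. In a single-centre convenience sample, another unit cannot judge whether the result applies to its own patients unless age, frailty and limb severity are described.

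**Working it through.** **The plan's own figure.** The only arithmetic in the plan is recruitment: 3 clinics × 3 to 4 new patients = 9 to 12 per week, so 90 to 120 in 10 weeks. This agrees with section 7.2 and does not bear on the point. No loss rate, effect size or SD is given, so what follows is illustration.

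**Numbers at risk.** With an assumed loss of 10% to 40%, 50 enrolled patients leave 45 to 30, and 100 leave 90 to 60.

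**Bias in the completers' mean.** Take a frail share of 0.5 (the Background's upper figure). Let r be retention and d the mean change, with N for non-frail and F for frail.

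- True mean = 0.5·dN + 0.5·dF
- Completers' mean = (0.5·rN·dN + 0.5·rF·dF) / (0.5·rN + 0.5·rF)

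All r and d values are assumed.

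| rN / rF | dN / dF | True | Completers | Bias |
|---|---|---|---|---|
| 0.8 / 0.5 | 0.15 / 0 | 0.075 | 0.060/0.65 = 0.092 | 0.017 |
| 0.8 / 0.5 | 0.15 / -0.05 | 0.050 | 0.0475/0.65 = 0.073 | 0.023 |
| 0.9 / 0.7 | 0.15 / 0 | 0.075 | 0.0675/0.80 = 0.084 | 0.009 |
| 0.9 / 0.7 | 0.15 / -0.05 | 0.050 | 0.050/0.80 = 0.0625 | 0.0125 |
| 0.9 / 0.7 | 0.12 / 0.02 | 0.070 | 0.061/0.80 = 0.076 | 0.006 |
| 0.9 / 0.6 | 0.12 / 0.02 | 0.070 | 0.060/0.75 = 0.080 | 0.010 |
| 0.9 / 0.5 | 0.12 / 0.02 | 0.070 | 0.059/0.70 = 0.084 | 0.014 |

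**What baseline EQ-5D can do.** For the last three rows, a large simulation assumed baseline means of 0.35 (frail) and 0.45 (non-frail), baseline SD 0.25, and a slope of change on baseline of -0.3 within each group.

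- Mean baseline in patients lost and kept was 0.376 v 0.407, 0.370 v 0.410 and 0.368 v 0.415. The planned data could therefore show a difference.
- Adjusting the change for baseline EQ-5D alone gave 0.078, 0.082 and 0.088 against a true 0.070, so the bias was not removed.
- Adding recorded frailty gave 0.070 in all three. Full recovery follows from assuming that loss depends on frailty alone.

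**Which adjustment works.** For the first two rows, a mixed model with frailty as a main effect only still gave roughly 0.09 against 0.075 and 0.07 against 0.050 (large simulated sample, assumed between- and within-person SDs of 0.18). Most of the bias stays because such a model forces one common change on both groups. Letting the change differ by frailty and averaging over all enrolled patients targets the right value: 0.5 × 0.15 + 0.5 × 0 = 0.075 in the first row. Response weights do the same: (0.40/0.8 × 0.15 + 0.25/0.5 × 0) / (0.40/0.8 + 0.25/0.5) = 0.075.

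**The case against.** A reader might infer that selective loss could be neither detected nor corrected at all. The protocol does not support that. Baseline EQ-5D is asked of every consenting patient and linked through the registry, so a limited check and some conditioning are possible.

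The absence is also partly read from silence. Section 5.1 does not say that nothing else is collected, section 5 records unspecified patient details on a register, and the restriction in section 8.4 concerns purpose rather than content. The research team provide these patients' care (section 7.3), so the items could be retrieved. This stands as far as it goes, but no extraction is planned and the stated purpose would not cover it.

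A reader might also infer that frail patients will be the ones lost. The Background ties frailty to treatment risk, not to non-response. Sections 5.1, 7.1.2 and 7.4 allow prompting by carers or relatives, and section 5.1 allows completion by researchers, which may help frail participants most. Selective loss is therefore plausible but not established.

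The illustrated bias is small beside sampling error. With an assumed SD of change of 0.25 to 0.30, the standard error runs from 0.25/√80 = 0.028 (80% of 100 kept) to 0.30/√32.5 = 0.053 (65% of 50 kept), and every bias shown is below that. This limits the weight of the point. It does not remove it, because the confidence interval would not reflect the bias.

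**Conclusion.** The point holds in limited form. From the data listed, patients lost and kept can be compared on baseline EQ-5D but not on age, frailty, diabetes or limb severity, and the change cannot be adjusted for those characteristics. If frailty drives the loss, baseline EQ-5D may not remove the bias.

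The size is unknown. The illustrations give 0.006 to 0.023 EQ-5D units, resting on assumed retention and change in each group and on a frailty share taken at the protocol's upper figure. They should not be read as a forecast that the reported improvement will be inflated by a particular percentage; nothing in the protocol fixes the loss rate or how change differs by frailty. The study can run as planned. This is a cheap improvement to what it collects, best made before enrolment.

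**What to change.** In section 5.1, add a short baseline record taken from the clinic notes at the first appointment and held under a study number: age band, sex, Rockwood score, diabetes, and tissue loss or rest pain. Amend the *solely* sentence in section 8.4 and the consent wording to match.

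Use the record to describe the cohort and to compare completers with non-completers at each follow-up. Beside the complete-pairs result, give one sensitivity estimate of the change, using either response weights or a covariate-by-time term (for example frailty) averaged over all enrolled patients. Entering covariates as main effects only is not enough. With 50 to 100 patients, keep to one or two covariates; more would be unstable. The modelling detail can sit in a statistical analysis plan, but the fields have to be in the protocol.

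Cost: about five fields per patient from notes the team already sees, one amendment to the ethics committee, a consent sentence, a little more personal data held, and a slightly less precise sensitivity estimate.
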